9.5 Analysis of blood samples

Blood samples collected at the respective time points will be prepared under standard laboratory protocols, blood and its derived components will be aliquoted and stored, as necessary, in appropriate conditions for further analyses. The samples will be analysed for known and novel biomarkers related to coronary artery disease and myocardial infarction, using techniques such as enzyme immunoassay, flow cytometry etc. Samples may be assayed using novel platforms to investigate the potential utility against the existing techniques. Samples may be stored and sent to other centres, outside the UK, for specific analyses, according to the availability of specialist techniques. Depending on specific informed consent being given by participants, blood will be stored for DNA extraction and future genetic analysis, including typing of SNPs and for whole genome analysis. Specific genetic variants may be used to guide invitations to participate in future studies.

9.6 Analysis of particulate debris

Intracoronary thrombus / plaque material obtained with the use of thrombus aspiration at any stage of the procedure will be prepared under standard laboratory protocols and stored at -80°C for further analyses. Snap frozen debris may be analysed using immunohistochemical stains, including antibodies to CD68, smooth muscle actin, CD3, and CD20, Tissue Factor [24], Vascular Endothelial Growth Factor (VEGF) [25], MMPs 2 and 9 [26], cellular proliferation and apoptosis [27-29]. Samples may also be analysed by extraction of mRNA for RT-PCR, or for levels of proteins/lipids using proteomics/lipidomics approach or other molecular markers using novel technologies.

10. IDENTIFICATION & DESCRIPTION OF THE INVESTIGATIONAL DEVICE

10.1 Device description

The PICSO Impulse System consists of the PICSO Impulse console (101.100.000.000) and PICSO impulse catheter (300.100.000.010) by Miracor Medical Systems ([name]).

PICSO Impulse Console

PICSO Impulse Catheter

Each PICSO Impulse catheter will have a serial number, which will be recorded for traceability during and after completion of the study.

The PICSO Impulse catheter presents a balloon at the distal end. The balloon inflates and deflates cyclically once deployed in the coronary sinus, leading to intermittent coronary sinus pressure increase. This intermittent increase in coronary sinus pressure leads to an improved perfusion of the ischemic

area with potential benefit in terms of myocardial salvage through 3 mechanisms: 1) redistribution of blood flow from the remote myocardium to the border zone of the ischemic myocardium [14]; 2) enhanced wash out of noxious, inflammatory factors and embolic material across the microvascular bed (suction effect upon balloon release) [15]; 3) improvement in collaterals through release of vascular growth factors as consequence of venous pressure increase [16-17].

The PICSO Impulse catheter is a 8F double lumen catheter with a 15.5x20mm long balloon at the distal end. The catheter is connected to the console through two pneumatic tubes in which helium is shuttled to and from the balloon. In addition, the coronary sinus pressure is monitored through the center lumen of the catheter. The catheter is placed in the coronary sinus over a 0.025' wire by a 8.5Fr pre-shaped delivery long steerable sheath (Oscor Destino Steerable Sheath DS856750/22) inserted in the femoral vein. Femoral vein access is obtained as routine practice according to Seldinger technique. Once the catheter is placed, the guidewire is removed and the steerable sheath is retracted in the right atrium for support. PICSO deployment median time has been estimated to be of 12 minutes (Interquartile Range 9-18 minutes)

The PICSO Impulse Catheter is then connected to the PICSO Impulse console. The PICSO Impulse Console automatically operates the PICSO Impulse Catheter. The balloon is intermittently inflated and deflated using helium, based on coronary sinus pressure and synchronized with the ECG. The monitor displays the inflation/ deflation state of the balloon, as well as trend graphs and time counters; Live graphs display curves and numeric values of ECG, coronary sinus pressure, aortic pressure and auxiliary input. It is easy to use and provides direct feedback on the patient's individual therapy using the 'PICSO Dose', which is defined as the sum of the coronary sinus pressure modulation for all PICSO cycles applied. All data are automatically stored and can be retrieved for later analysis for each patient. The unit is transportable and runs on battery supply if needed during patient transportation.

Once the PICSO Impulse catheter is connected to the consoled, by activating the "START" button, the distal balloon will be cyclically inflated. Each cycle starts with a balloon inflation triggered by QRS

complex on ECG monitoring. During balloon inflation coronary sinus pressure will progressively increase till reaching a plateau, then coronary sinus occlusion is stopped by balloon deflation. For security, each balloon inflation has a maximum limit of 30 seconds in duration. The deflation interval between two cycles has a minimum duration of 3 seconds.

In the OxAMI-PICSO the PICSO Impulse system will be adopted in a highly selected population of patients with ST elevation myocardial infarction, characterized by a possibly impaired microvasculature impairment at the time of the PCI, as expressed by a prestenosing elevated index of microcirculatory resistance (> 40). The aim is to assess the extent of infarct size after 24-48 hours in such specific group of patients. Propensity-score matched historical patients from the ongoing OxAMI study will be controls in the OxAMI-PICSO study.

All the investigators using the PICSO device will undergo a specialist training programme completion, including the performance of the first cases under the supervision of a proctor expert. Educational training sessions for use of the PICSO will be provided to all clinical staff (nurses, radiographers, physiologists) involved in the care of patients who have received PICSO.

10.2 Device Safety

PICSO treatment is safe. Potential complications associated to PICSO may include:

- a) Bleeding due to damage to the coronary sinus where the PICSO catheter is placed
- b) Bleeding in the groin from the femoral vein access.
- c) Long term blockage of the coronary sinus where the PICSO catheter sits.
- d) Helium leak from the catheter into the blood. A leak of helium into the patient could occur with a balloon rupture or hole. However the risk is significantly mitigated since the system can automatically detect any leakage and stop the procedure. The maximum helium volume that could enter the patient using the PICSO system is less than 10 ml. This volume is approximately 1/3 of the volume that could leak from a bursting intra-aortic balloon pump (IABP) catheter, that are used in routine clinical practice in the aorta (i.e arterial circulation), whereas the PICSO catheter is used exclusively in the venous

circulation.. A helium leak from the PICSO system is therefore regarded to constitute a low risk to the patient.

Data about PICSO are continuously increasing and in the two main studies performed in man so far (PREPARE-PICSO and PREPARE-RAMSES) only one procedure adverse event (tamponade secondary to coronary sinus perforation) has been described. This rate (<3%) of complication is further lower than that associated to the routine elective electrophysiological procedures to the coronary sinus in the context of tachycardia ablation or cardiac resynchronization therapy.

It is possible that the PICSO balloon may be dislodged from the coronary sinus into the right atrium. This event has no known safety implications for the patients, but it may affect the efficacy of the PICSO treatment. The PICSO console will detect the occurrence of such event and alert the clinical team. In such a scenario balloon repositioning will only be considered if the treatment time-interval is less than 60 minutes. In order to minimize the risk for the patient, repositioning will be performed under fluoroscopic guidance in the catheterization laboratory. Once the balloon is repositioned, the PICSO treatment will be continued to achieve a minimum total treatment time of 60 minutes to a maximum of 90 minutes from the time of stent deployment.

All the investigators using the PICSO device will undergo a specialist training programme completion, including the performance of the first cases under the supervision of a proctor expert. Educational training sessions for use of the PICSO will be provided to all clinical staff (nurses, radiographers, physiologists) involved in the care of patients who have received PICSO. Patients undergoing PICSO treatment will be strictly monitored, according to the standard clinical care guidelines, during and after the PICSO treatment in order to minimize or to early detect possible issues associated to the treatment. After the procedure, when the PICSO treatment is still ongoing, the patients will be monitored in the Recovery Assessment Area in order to guarantee a rapid access to the Catheterization Laboratory, if required.

The additional x-rays used for the placing of the device is extremely low in the context of the exposure associated to the standard primary PCI procedure. The radiation dose associated with the placement

of the device is estimated to be 4.3 mSv, which is approximately equivalent to 22 months exposure to UK background radiation. This may theoretically be associated with an increased lifetime risk of developing a cancer of 0.06%. This compares with the risk of developing a cancer in the general population of around 30% to 40%. So overall this represents a very small addition to the underlying cancer risk from all causes.

The radiation exposure in case of repositioning the PICSO balloon is estimated to be less than that associated with the device implantation. Therefore patients undergoing repositioning would have a global radiation dose associated to the PICSO device of no more of 8 mSv.

10.3 Device Accountability

PICSO Impulse console and PICSO Impulse catheter will be provided by Miracor Medical Systems. We will be documenting the number of devices, with their lot numbers, that will be shipped to the John Radcliffe Hospital. PICSO Impulse console will be placed in the Catheterization Laboratory of the John Radcliffe Hospital, connected to electric supply in order to assure full charge of the battery. After their delivery, the PICSO Impulse catheters will be stored in the storage room of the Catheterization Laboratory of the John Radcliffe Hospitals and kept in a cool, dry place.

We will document on the CRF the LOT number and expiry date for each balloon for each patient.

11 SAFETY REPORTING

11.1 Definitions

Adverse Event (AE)	Any untoward medical occurrence, unintended disease or injury or any untoward clinical signs (including an abnormal laboratory findings) in participants, users or other persons whether or not related to the investigational medical device. This includes events related to the
--------------------	--

	investigational device or comparator, events related to the procedures involved (any procedure in the protocol). For users or other persons this is restricted to events related to the investigational medical device.
Adverse Device effect (ADE)	An adverse event related to the use of an investigational medical device. This definition includes any events resulting from insufficient or inadequate instructions for use, deployment, implantation, installation, or operation, or any malfunction of the investigational device. This definition also includes any event resulting from user error or form intentional misuse of the investigational device.
Serious Adverse Event (SAE)	An adverse event that: 
 • Led to death • Resulted in serious deterioration in the health of the subject that: 
 ○ resulted in a life-threatening illness or injury ○ resulted in a permanent impairment of a body structure or a body function ○ required in-patient care or prolongation of hospitalisation ○ resulted in medical or surgical intervention to prevent life-threatening illness or injury or permanent impairment to a body structure or a body function.

	
This includes device deficiencies that might have led to a serious adverse event if:
 
 a) suitable action had not been taken or b) intervention had not been made or c) circumstances had been less fortunate. 
These are handled under the SAE reporting system.
 
Planned hospitalisation for a pre-existing condition, or a procedure required by the trial protocol, without serious deterioration in health, is not considered a serious adverse event.

Serious Adverse Device Effect (SADE)	
Any untoward medical occurrence that can be attributed wholly or partly to the device, which resulted in any of the characteristics of a serious adverse event as described above.
 
Unanticipated Serious Adverse Device Effects (USADE)
 
Any serious adverse device effect which, by its nature, incidence, severity or outcome, has not been identified

Device deficiency	
Inadequacy of a medical device with respect to its identity, quality, durability, reliability, safety or performance. Device deficiencies include malfunctions, use errors and inadequate labeling.
 
Device deficiencies that did not lead to an adverse event, but could have led to a medical occurrence if suitable action had not been taken, or intervention had not been made or if circumstances had been less fortunate

User error	Act or omission of an act that results in a different medical device response than intended by the manufacturer or expected by the user. Use error includes slips, lapses and mistakes. An unexpected physiological response of the subject does not itself constitute a use error.
------------	---

Severity definitions

The following definitions will be used to determine the severity rating for all adverse events:

Mild: awareness of signs or symptoms, that does not interfere with the subject's usual activity or is transient that resolved without treatment and with no sequelae.

Moderate: a sign or symptom, which interferes with the subject's usual activity.

Severe: incapacity with inability to do work or perform usual activities.

11.2 Causality

The relationship of each adverse event to the trial device may be determined by the manufacturer and/or a medically qualified Investigator according to the following definitions:

Not related: The event is clearly related to other factors such as the patients/participants clinical condition, therapeutic intervention, concomitant medication.

Unlikely: The event is probably produced by other factors such as the patients/participants clinical condition, therapeutic intervention, concomitant medication and does not follow a known response pattern to the device

Possibly: The event follows a reasonable temporal relationship from the time of placement/administration and/or follows a known response pattern to the device but could have been caused by other factors such as the patients/participants clinical condition, therapeutic intervention, concomitant medication.

Most probable: The event follows a reasonable temporal relationship from the time of placement/administration and/or follows a known response pattern to the device and could not have been caused by other factors such as the patients/participants clinical condition, therapeutic intervention, concomitant medication. Further the event immediately follows the administration/placement of the device and improves on stopping or removing the device.

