5. OBJECTIVES AND OUTCOME MEASURES/ENDPOINTS

Objectives	Outcome Measures/Endpoints
------------	----------------------------

Primary Objective
 
To assess the impact of PICSO on coronary physiology parameters, on infarct size, on myocardial salvage and on microvascular obstruction at CMR in a selected population of STEMI patients at higher risk of no reflow and with the theoretical prerequisites that make more likely to respond to PICSO treatment. The control group will be represented by a highly matched group of patients from the ongoing Ox-AMI (Oxford Acute Myocardial Infarction) project (Ethics Ref 11/SC/0397), who have undergone all other aspects of the study protocol, including assessment of coronary physiology at 24 hours post primary PCI, 24-48 hours and 6 months CMR, but who have not received PICSO treatment.
	
Area at risk, Infarct size, Myocardial salvage and microvascular obstruction measured by cardiac magnetic resonance at 24-48 hours

Secondary Objectives
 
The OxAMI-PICSO study aims to evaluate the utility of individual biomarkers (blood components derived substances from cells, DNA, plasma etc) in the assessment of coronary artery disease and myocardial infarction. The OxAMI-PICSO may show also how these individual biomarkers may be modified by PICSO treatment.
	
Coronary flow reserve (CFR), Fractional Flow reserve (FFR), index of microcirculatory resistance (IMR) measured at 24 hours after PCI.
 
Infarct size and microvascular obstruction extent measured by cardiac magnetic resonance at 6 months
 
Individual Biomarkers related to coronary artery disease/myocardial infarction at three time points (PCI, 24/48 hours after PCI and 6 months). These include: blood biomarkers of myocardial injury, metabolism and inflammation.

Tertiary Objectives
 
To evaluate the rate of PICSO failure deployment, coronary sinus complications, and additional time and radiation exposure associated to for PICSO deployment
	
Rate of PICSO failure deployment
 
Rate of coronary sinus complications: perforation, dissection, thrombosis
 
Time for PICSO deployment / additional screening time and radiation dose

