11.3 Procedures for Recording Adverse Events

All adverse events (including ADEs) and device deficiencies occurring during the course of the study will be recorded on the CRF whether or not attributed to the trial device. The information recorded will include but not be limited to:

- A description of the event
- The dates of the onset and resolution
- Action taken
- Outcome
- Assessment of relatedness to the device
- Whether the AE is serious or not
- Whether the AE arises from device deficiency
- Whether the AE arises from user error

The severity of events will be assessed on the following scale: 1 = mild, 2 = moderate, 3 = severe.

AEs/ADEs considered related to the device as judged by a medically qualified investigator or the Sponsor will be followed either until resolution, or the event is considered stable.

It will be left to the Investigator's clinical judgment to decide whether or not an AE/ADE is of sufficient severity to require the participant's removal from treatment. A participant may also voluntarily withdraw from treatment due to what he or she perceives as an intolerable AE/ADE. If either of these occurs, the participant must undergo an end of trial assessment and be given appropriate care under medical supervision until symptoms cease, or the condition becomes stable.

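### The top causality level in 11.2 requires improvement on device removal, so a lasting coronary sinus injury can be rated no higher than Possibly or fits no level; 11.2 also lets the manufacturer rate without an investigator

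*Combined protocol and SAP*

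**What the plan says.** Section 11.2 sets out four levels: *Not related*, *Unlikely*, *Possibly* and *Most probable*.

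- *Unlikely* is for events that other factors probably produced and that the plan describes with "does not follow a known response pattern to the device".
- *Possibly* needs a reasonable time relationship, or that the event "follows a known response pattern to the device but could have been caused by other factors".
- *Most probable* needs the same timing or pattern, rules out other causes altogether, and then adds: "Further the event immediately follows the administration/placement of the device and improves on stopping or removing the device".

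On who decides, 11.2 states: "The relationship of each adverse event to the trial device may be determined by the manufacturer and/or a medically qualified Investigator". Section 11.3 describes the follow-up rule differently: "AEs/ADEs considered related to the device as judged by a medically qualified investigator or the Sponsor will be followed either until resolution", or until the event is considered stable.

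The coronary sinus harms are named elsewhere. Section 5 has the tertiary outcome "Rate of coronary sinus complications: perforation, dissection, thrombosis". Section 10.2 lists bleeding from coronary sinus damage and long-term blockage among the potential complications, and reports one tamponade after coronary sinus perforation in the two main human studies so far.

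**The concern.** Improvement on withdrawal suits reversible effects. It does not suit structural injury, and requiring immediate onset does not suit a thrombosis or blockage that develops later. The harms that the protocol itself associates with the device are therefore those that its top causality level handles worst.

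The relatedness rating has consequences. It is an entry on the CRF (11.3). It decides whether a non-serious event carries a follow-up commitment (11.3). Attribution to the device separates an AE from an ADE, and an SAE from a SADE or USADE (11.1), and SADEs and USADEs go to the manufacturer (11.4). If raters must improvise a level for a clear device injury, these classifications will vary from one rater to another.

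The second issue is independence. Under 11.2 a rating by the manufacturer alone complies with the protocol. The same company supplies the catheters, the console and an unrestricted grant (17.1). Nothing says what happens if the manufacturer and the investigator disagree.

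**Working it through.** No arithmetic applies. The check sets two cases against the written conditions of each level.

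- **Case A:** a coronary sinus injury that persists after the catheter is removed, with no other possible cause.
- **Case B:** the same injury where another cause is arguable. Section 8.3.3 allows blood to be taken with a separate coronary sinus sampling catheter, so this is realistic.

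Both cases are taken to follow a known response pattern, because 10.2 lists coronary sinus damage and long-term blockage as potential complications. Section 11.2 does not define the term, so this is an assumption.

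| Level | Conditions (paraphrased) | Case A | Case B |
|---|---|---|---|
| *Not related* | Clearly due to something else | Fails | Fails: another cause is arguable, not clear |
| *Unlikely* | Probably due to something else, and outside the known pattern | Fails on both | Fails: within the known pattern |
| *Possibly* | Timing and/or known pattern, and another cause could be responsible | Fails on the other cause | Met |
| *Most probable* | Timing and/or known pattern, no other cause possible, immediate onset, improvement on removal | Fails on improvement | Fails on other cause and on improvement |

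Case A meets 0 of 4 levels. Case B meets exactly one, *Possibly*. A thrombosis of late onset with no other cause also fails the top level on the immediacy condition.

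**With the added sentence deleted.** Case A then meets *Most probable* in full. Case B stays at *Possibly*, because the top level still excludes any other cause. Deletion closes the gap but does not settle whether Case B counts as device-related. No section says which levels do, so that rule has to be written as well.

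**Who decides.** Section 11.2: "may be determined by the manufacturer and/or a medically qualified Investigator according to the following definitions". Section 11.3: "AEs/ADEs considered related to the device as judged by a medically qualified investigator or the Sponsor". The first allows the manufacturer alone, the investigator alone, or both. The second names the investigator or the Sponsor and leaves the manufacturer out. Section 11.4 lists Sponsor and manufacturer as separate recipients, so they cannot be read as the same party.

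**What depends on the rating, and what does not.**

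- Depends on it: the CRF relatedness entry and follow-up of non-serious events (11.3); ADE, SADE and USADE status (11.1); reporting of device effects to the manufacturer where there is no immediate risk (11.4).
- Does not depend on it: recording of adverse events (11.3); follow-up of SAEs and two-day reporting of immediate-risk events (11.4); the tertiary complication rate (5).

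**The case against.** The strongest reply is that little harm follows. All adverse events are recorded regardless of attribution, and all SAEs are followed to resolution. Serious events posing an immediate risk reach the manufacturer, the competent authority and the REC without any relatedness test. The hospital Trust reviews all SAEs and SADEs quarterly and cumulatively (11.6). The SADE definition accepts partial attribution and does not ask for improvement on removal. All of this stands, and it confines the point to the classification and reporting items listed above.

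Three stronger readings are tempting, and the documents support none of them.

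- A reader might infer that these injuries cannot be rated above *Unlikely*. They can: the removal condition belongs only to the top level, and *Possibly* ranks higher than *Unlikely* and accepts a known pattern when another cause is arguable. A coronary sinus injury within the known pattern does not meet *Unlikely* at all, so the wording does not push it down to that level.
- A reader might infer that only the manufacturer decides. The wording equally allows the investigator alone, and the follow-up rule in 11.3 does not rely on the manufacturer.
- A reader might divide one event by 25 and say that each re-rating moves a device-related rate by 4 percentage points. The plan defines no such rate. Its 25 are patients treated who also complete six-month follow-up (8.4), so the number exposed to the device may be larger.

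It can also be said that a sensible investigator would choose the nearest level. That may happen, but the protocol does not say which level is nearest, and *Possibly* would contradict the facts of Case A.

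**Conclusion.** The point holds in limited form. A lasting coronary sinus injury is capped at *Possibly* when another cause is arguable and has no level when none is possible. Sections 11.2 and 11.3 disagree on who judges relatedness, and 11.2 lets the manufacturer rate without an investigator.

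The size cannot be put as a number. The conclusion rests on two assumptions: the definitions are applied as written, and structural injuries of this kind need not improve when the catheter is withdrawn. Under a looser reading, Case A would be placed at one of the upper two levels at the rater's discretion, which makes ratings inconsistent without necessarily making them low. The documents do not show that events have been or will be under-rated.

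The change should be made because a stated rule fails for the device's own named harms and the repair is cheap. It does not bear on the primary analysis.

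**What to change.** 1. In 11.2, delete the sentence on immediate onset and improvement on removal, or limit it to reversible events by adding 'where applicable'. Deletion is cleaner, because the limited form would still hold back a reversible event of late onset.
2. State in 11.2 which levels count as device-related for the CRF, for ADE/SADE/USADE status and for follow-up, for example *Possibly* and *Most probable*.
3. Require a medically qualified investigator to assess every event. The manufacturer may add an opinion but may not lower the rating.
4. Reconcile 11.3 with 11.2 so that both name the same assessors.

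The cost is wording in two sections and an edit to the adverse event form. The downside is that slightly more events will be classed as device-related.
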